3.2. Disposition and baseline characteristics

Disposition of patients and baseline characteristics will be described by randomised treatment group, to assess their comparability, and overall.

3.2.1. Disposition of patients

Disposition of patients, including reasons for study*/treatment withdrawal**, will be summarized during the double-blind period, during the open-label period, and during the study (excluding extension period) overall as well as during the double-blind period and during the open-label period by visit, in the RS. The number and percentage of patients who completed the double-blind (resp. open-label) period before (resp. after) the initiation of COVID-19 Pandemic will be also provided.

Note:

- * Study withdrawal related to COVID-19 pandemic will be also described.
- ** Information related to treatment withdrawal will only be described for the double-blind period.

A listing of patients with treatment withdrawal but having completed the double-blind period as well as a listing of patients with a delay between the double-blind and open-label periods will be provided.

The number and percentage of patients entering in the extension period will be described in the RS.

In order to assess the drop-out pattern between the treatment groups, the time to premature IMP withdrawal in the double-blind period will be described overall and by reason (lack of efficacy or AE; other reasons of withdrawal), in the RS using a Kaplan-Meier analysis. Withdrawn and completed patients' characteristics during the double-blind will be described overall, in the RS, and their comparability at inclusion visits assessed.

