5.6.2. Procedure

The investigator must notify the sponsor of study withdrawals by entering data of the withdrawal visit in the e-CRF. The investigator must record the reason and the exact date of the premature discontinuation from the study in the e-CRF. If more than one reason is given, the investigator must indicate the main reason.

In case of premature discontinuation from the study a withdrawal visit will be done as soon as possible after the last dose intake and within one week at the latest

In the case of premature withdrawal of IMP due to an adverse event (event requiring immediate notification or not), the investigator must make every effort to collect the information relating to the outcome of the event. If necessary, the information will be collected afterwards (see section 8.9). This information is recorded in that part of the e-CRF which concerns adverse events. If the investigator cannot collect the information from a visit, he/she must collect it from the doctor ensuring the follow-up of the participant.

If the study is stopped / treatment is discontinued as a result of an event requiring immediate notification, the procedure described in Section 8.9.2.5 is to be implemented.

The dispositions to be taken after the IMP discontinuation are described in Section 6.5.

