1.3. Determination of sample size

The sample size was estimated to meet the primary endpoint defined as the change in CARS2 from baseline to 6 months using a two-sided Student's test.

With a total of 170 patients, statistical significance should be established with a power of 90% and a type-one error of 0.05 for an effect size of 0.5 between groups.

Assuming around 15% prematurely withdrawal rate, the total number of patients to be included is 200.

Missing data will be imputed using a reference based multiple imputation with a jump-to-reference approach or a standard multiple imputation depending on the reasons of withdrawal. Simulations were carried out to evaluate the impact of this procedure on power under various scenarios. The results on 1000 simulations have shown that power does not drop under 80% in the worst-case scenario.

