Primary analysis: bumetanide will be compared to placebo on the primary efficacy endpoint in the RS, using a General Linear Model (see Appendix 5.1.1.1) including the fixed, categorical effect of treatment, gender and country as well as the continuous fixed covariate of baseline value.

GENERAL LINEAR MODEL (ANCOVA): change = baseline country gender treatment [1]

The assumptions underlying the model, as for instance, the normality and homoscedasticity of residuals and detection of outliers, will be checked.

Missing data handling:

- For all study premature withdrawals due to other reasons as well as for study premature withdrawals due to lack of efficacy or AE in placebo arm, missing data will be imputed in both arms using a multiple imputation based on similar patients in the same treatment arm (missing at random assumption).
- For study premature withdrawals due to lack of efficacy or AE in S95008 arm, missing data will be imputed using a reference based multiple imputation with a jump-to-reference approach (*missing not at random assumption*).
Missing data as well as data considered as missing for the primary analysis due to the strategy used to handle intercurrent event will be imputed in the same way.

Multiple imputation inference involves 3 consecutive phases.

1/ Imputation step:

A total of 100 imputed complete data sets will be generated.

The imputation step of missing data with a monotone pattern will be separated in several sequences:

- For all patients with study or drug premature withdrawals due to other reasons as well as for patients with study or drug premature withdrawals due to lack of efficacy or AE in placebo arm, the regression method (adjusted on the same covariates as the model [1] and considering all longitudinal data of planned visits) will be used to impute missing data (*i.e.* based on patient completers under corresponding treatment arm).
- For patients with study or drug premature withdrawals due to lack of efficacy or AE in S95008 arm, the imputation step will be done sequentially for each time point t separately (W4, W12 and W26) based on placebo patients with non missing data at the timepoint t . The regression method will be adjusted on the same covariates as model [1] except the treatment variable (which is a modified variable in order to consider the placebo data as reference for imputation) and considering all longitudinal data of planned visits up to timepoint t .

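### Kaplan-Meier curves of IMP withdrawal by reason will, as usually run, slightly overstate the share withdrawing for a reason; cumulative incidence curves would agree with the overall curve and the disposition counts

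*SAP*

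**What the plan says.** SAP 3.2.1 sets out the aim and the quantity: "In order to assess the drop-out pattern between the treatment groups, the time to premature IMP withdrawal in the double-blind period". In the same sentence, the method is that this time "will be described overall and by reason (lack of efficacy or AE; other reasons of withdrawal), in the RS using a Kaplan-Meier analysis". The section does not say how a child who stops for the other reason enters a reason-specific curve, and it names no competing-risk estimator.

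The same section also plans a summary of the reasons for treatment withdrawal in the double-blind period, in total and by visit, in the randomised set. SAP 3.2 adds: "Disposition of patients and baseline characteristics will be described by randomised treatment group, to assess their comparability, and overall".

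The two reason groups are exhaustive and exclusive. On recording, Protocol 5.6.2 says of discontinuation: "If more than one reason is given, the investigator must indicate the main reason". That sentence is written for discontinuation from the study, but a child can stop the IMP definitively only once.

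SAP 3.4.2.1 uses the same grouping for the primary analysis: "For study premature withdrawals due to lack of efficacy or AE in S95008 arm, missing data will be imputed using a reference based multiple imputation". Other-reason withdrawals in that arm, and all placebo withdrawals, are imputed under missing at random. SAP 3.4.1 allows no p-value outside the primary analysis. The only withdrawal rate in the documents is in SAP 1.3 (and Protocol 10.1): "Assuming around 15% prematurely withdrawal rate, the total number of patients to be included is 200".

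**The concern.** Kaplan-Meier by reason, with the other reason censored, estimates withdrawal in a setting where the other reason does not exist. The section's stated aim is different: it wants the drop-out pattern that actually occurred in each arm. Three planned displays would then disagree. The two reason curves would not add up to the any-reason curve, and neither need equal the percentage for that reason in the disposition table.

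The grouping is also the one that separates jump-to-reference from missing-at-random imputation in the bumetanide arm. A reader is likely to use the curves to judge how many children fall under each rule and when. At stake is a clear and consistent description of drop-out, not the trial's result.

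**Working it through.** **Inputs.** Total withdrawal F = 15% (SAP 1.3), which does not say whether study or IMP withdrawal is meant; it is used here for IMP withdrawal. Two exclusive reasons (SAP 3.2.1). Fixed follow-up, W000 to W026 (SAP 1.2.1). Loss to follow-up is itself listed as a ground for discontinuation (Protocol 5.6.1), so it falls under other reasons and there is little other censoring. The split by reason and by arm is not in the documents, so every split below is an assumption, as are rates other than 15%.

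**The plan's own figure.** SAP 1.3 assumes "a power of 90% and a type-one error of 0.05 for an effect size of 0.5 between groups". Per arm, n = 2(1.960 + 1.282)²/0.5² = 84.1, rounded up to 85, so 170 in total (exact t-test power 0.8999). Then 170/(1 − 0.15) = 200. Both planned numbers reproduce.

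**Why the curves do not add up.** Let K1 and K2 be one minus Kaplan-Meier for each reason, with the other reason censored. Apart from same-day ties, the any-reason Kaplan-Meier curve is the product of the two: 1 − F = (1 − K1)(1 − K2). Hence K1 + K2 = F + K1·K2. Whenever both reasons occur, the sum exceeds F by K1·K2.

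**Size per curve.** With constant cause-specific hazards and share s for one reason, the cumulative incidence at W026 is sF and K = 1 − (1 − F)^s. For example, 1 − 0.85^0.5 = 7.80% against 0.5 × 15% = 7.50%.

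| Total F | Split | Cumulative incidence | 1 − KM | Excess per curve (points) | Sum of 1 − KM |
|---|---|---|---|---|---|
| 15% (SAP) | 50/50 | 7.50% + 7.50% | 7.80% + 7.80% | 0.30 | 15.6% |
| 15% (SAP) | 25/75 | 3.75% + 11.25% | 3.98% + 11.48% | 0.23 | 15.5% |
| 20% (assumed) | 50/50 | 10% + 10% | 10.56% + 10.56% | 0.56 | 21.1% |
| 30% (assumed) | 50/50 | 15% + 15% | 16.33% + 16.33% | 1.33 | 32.7% |
| 40% (assumed) | 50/50 | 20% + 20% | 22.54% + 22.54% | 2.54 | 45.1% |

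**Order of withdrawals.** At F = 15%, split 50/50, suppose every withdrawal for one reason comes first. The earlier curve is exact at 7.50%. The later one is 7.5/(100 − 7.5) = 8.11%, an excess of 0.61 points. So timing decides which curve carries the excess.

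**Between-arm contrast** (AE or lack of efficacy + other, bumetanide against placebo; all assumed):
- Same pattern in both arms: no distortion.
- 12% + 8% against 4% + 6%: the AE or lack-of-efficacy difference moves from 8.0 to 8.4 points, and the other-reason difference from 2.0 to 2.4.
- 20% + 10% against 5% + 10%: the other-reason curves read 1 − 0.70^(1/3) = 11.21% and 1 − 0.85^(2/3) = 10.27%. A true difference of zero shows as 0.9 points.

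**Scale.** With about 100 children per arm, the standard error of a 7.5% proportion is √(0.075 × 0.925/100) = 2.6 points, roughly nine times the 0.30-point excess.

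**The case against.** The strongest reply is that nothing depends on these curves. They are descriptive and carry no p-value, and the same section already supplies crude proportions by reason and visit, shown by arm, with no competing-risk problem. Reason-specific Kaplan-Meier is also a recognised display of cause-specific withdrawal intensity, and it misleads only if read as a share of children. At 15% the excess is under a third of one child per 100. All of this stands, and it is why the point is minor. It does not remove the disagreement between planned displays of the same data.

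A second reply is that censoring of the other reason is inferred. That also stands. If children who stopped for the other reason were kept at risk to W026, the curve would equal the cumulative incidence, given no other censoring. The SAP's silence leaves this to the programmer.

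Three stronger readings are tempting, and the documents or the arithmetic do not support them:
- *The curves affect the primary result.* A reader might infer this from the shared grouping. But SAP 3.4.2.1 and 5.1.2 impute from each child's own recorded reason, and the curves feed no estimate or test. Reason changes the imputation only in the bumetanide arm.
- *Both curves are always overstated.* This needs withdrawals for the two reasons to interleave in time. If one reason always comes first, its curve is exact.
- *The arm with more withdrawals of the other type shows the larger excess.* This holds only if withdrawal for the reason in question is held fixed. At 15% total, raising the other reason from 7.5% to 11.25% lowers the excess from 0.30 to 0.23 points.

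**Conclusion.** The point holds as a minor reporting matter. Under the usual censoring of the other reason, the reason-specific curves overstate the share withdrawing for a reason whenever withdrawals for the other reason come earlier, and together they exceed the any-reason curve. At the one withdrawal rate the documents give, the excess is about 0.2 to 0.3 points per curve with constant hazards, and at most about 0.6 points for one curve in an even split. Distortions near 1 point or more, in a curve or in the between-arm contrast, need withdrawal well above 15% in at least one arm, which is an assumption. The any-reason curve, the disposition counts, the imputation and the primary analysis are unaffected.

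**What to change.** In SAP 3.2.1, keep Kaplan-Meier by arm for time to IMP withdrawal for any reason. For the two reason groups, specify Aalen-Johansen cumulative incidence functions by arm, with the other reason group as a competing event and children still on IMP censored at the end of the double-blind period. The two curves then add up to the any-reason curve and, with no other censoring, end at the percentages in the disposition table. If cause-specific Kaplan-Meier curves are kept as well, state that the other reason is censored and that the curve is not a proportion of children.

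The cost is one sentence in the SAP and a small programming change. It needs no new data and changes no other analysis.

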3.2.2. Protocol deviations

Protocol deviations before or at inclusion, as well as after inclusion, will be described by category of important deviations (based on [ICH E3 guideline](#) and [ICH E3 Q&A](#)) during the double-blind period, during the open-label period, and during the study (excluding extension period but including the deviations occurring between double-blind and open-label periods when there is a delay between them) in the RS.

The same analysis will be performed for protocol deviations after the initiation of COVID-19 Pandemic (*i.e. after start of COVID-19 impact*) (before or at inclusion, as well as after inclusion).

3.2.3. Demographic data and other baseline characteristics

Demographic data and other baseline characteristics such, vital signs, history and diagnosis of the disease will be described in the RS.

Baseline value of efficacy endpoints will also be described in the RS:

- CARS2: total raw score, version of the questionnaire used (ST or HF), severity of ASD.
- SRS-2 total raw score and core symptoms A and B.
- CGI-S score.
- Vineland adaptative behaviour scale: VABS II Adaptative Behavior Composite score, standard domains scores.

The Columbia-suicide severity rating scale children (C-SSRS-C) base during lifetime and during the past 6 months will be also described in the RS.

Moreover all specific (resp. non-specific) previous treatments taken within the 6 months before selection will be described in the RS, by ATC code; as well as all medical history other than studied disease and surgical or medical procedures history, by primary system organ class and preferred term. Previous therapies by ATC code for the disease will also be described in the RS.

3.3. Treatments of patients

3.3.1. Extent of exposure and treatment compliance

Extent of exposure (follow-up duration (month), treatment duration (month), treatment exposure (month)) and treatment compliance (%) will be described in the SS for double-blind period, in the SSO for open-label period and in the SSC for the combined period.

It is of note that treatment duration will also be described in classes:

- For double-blind period and open-label period: (<4 weeks, [4 weeks; 12 weeks], > 12 weeks).
- For combined period: (< 26 weeks, [26 weeks; 38 weeks], and > 38 weeks).

3.3.2. Concomitant treatments and therapies

All specific (resp. non-specific) concomitant treatments taken at inclusion, during the double-blind (resp. open-label, combined) period, at the first IMP intake of the open-label period and after the last IMP intake of the double-blind (resp. open-label) period will be described in the SS (SSO when open-label and SSC when combined), by ATC code. Therapies for autism spectrum disorder will also be described at inclusion and during the double-blind period in the SS and during the open-label in the SSO and during the combined period in the SSC. The number and percentage of patients with at least one therapy of ASD will be described overall and by type of therapy at inclusion in the SS. The number and percentage of patients with at least one new added therapy / one modification in current therapy / one clinically relevant modification in therapy will be described overall and by type of therapy in each period.

3.3.3. Acceptability and palatability questionnaires

The acceptability and palatability questionnaires will be presented using descriptive statistics for the visit at which it has been collected (W026 or before in case of premature withdrawal) in the RS by treatment group (S95008 VS placebo) for the double-blind period.

3.4. Efficacy analysis

All efficacy analyses will be performed on the randomised set.

3.4.1. Statistical hypotheses

The hypotheses to be tested are:

Let μ_0 and μ_1 be the population means of the change from baseline of the CARS2 at W026 (primary endpoint) under placebo and bumetanide respectively. The statistical hypotheses that will be tested are:

$$H0: \mu_0 = \mu_1 \text{ (no difference between bumetanide and placebo)}$$

versus

$$H1: \mu_0 \neq \mu_1 \text{ (difference between bumetanide and placebo)}$$

The type I error of the statistical tests will be set at 5% (bilateral situation), which is consistent with the objective of demonstrating the superiority versus placebo (unilateral situation at 2.5%).

Similar hypotheses will also be considered for the secondary efficacy parameters. However, for all other analyses than the primary analysis, no p-value will be provided.

3.4.2. Primary efficacy endpoint

3.4.2.1. Primary analysis

Definition:

The primary estimand is defined according to the primary objective of the trial, which is to evaluate treatment effect:

- Taking into account the unfavorable outcome when patients are unable to continue taking the study drug due to an adverse event or for lack of efficacy.
- Independently of treatment discontinuations for non-medical reasons because those patients would have theoretically continued to be treated as planned in clinical practice.

The attributes of the primary estimand will be defined as following:

- Population: children and adolescents aged from 2 to less than 7 years old with Autism Spectrum Disorder.
- Variable: change in CARS2 total score from baseline to W026.
- Summary measure: difference in means.
- Intercurrent events:
 - Treatment discontinuation due to lack of efficacy or AE (*hypothetical strategy*):
 - For S95008 arm, the quantification of the treatment effect cannot ignore the situation where a patient can no longer tolerate or benefits from the treatment, from whom a continuation of the treatment would not be conceivable. Bumetanide is a treatment with a rapid onset and short duration of action. So, the assumption that the treatment benefit in patients who discontinue the active arm disappears immediately upon discontinuation is clinically meaningful. CARS2 values after this intercurrent event will be considered as missing and imputed using a reference based multiple imputation (“jump-to-reference” approach).
 - For placebo arm, it will be considered as if patients were stayed under placebo, and CARS2 values after the intercurrent event will be considered as missing and imputed using a multiple imputation (MAR approach).
 - Treatment discontinuation for other reason (*hypothetical strategy*): a reasonable question is what difference is attributable to treatment if no such events occurred namely if patients were stayed under their randomised treatment. CARS2 values after the intercurrent events will be considered as missing and imputed in both arms using multiple imputations (MAR approach).

Primary endpoint: the primary efficacy endpoint is defined as the change from baseline to W026 of the CARS2 total score.

Primary analysis: bumetanide will be compared to placebo on the primary efficacy endpoint in the RS, using a General Linear Model (see Appendix 5.1.1.1) including the fixed, categorical effect of treatment, gender and country as well as the continuous fixed covariate of baseline value.

GENERAL LINEAR MODEL (ANCOVA): change = baseline country gender treatment [1]

The assumptions underlying the model, as for instance, the normality and homoscedasticity of residuals and detection of outliers, will be checked.

Missing data handling:

- For all study premature withdrawals due to other reasons as well as for study premature withdrawals due to lack of efficacy or AE in placebo arm, missing data will be imputed in both arms using a multiple imputation based on similar patients in the same treatment arm (missing at random assumption).
- For study premature withdrawals due to lack of efficacy or AE in S95008 arm, missing data will be imputed using a reference based multiple imputation with a jump-to-reference approach (*missing not at random assumption*).
Missing data as well as data considered as missing for the primary analysis due to the strategy used to handle intercurrent event will be imputed in the same way.

Multiple imputation inference involves 3 consecutive phases.

1/ Imputation step:

A total of 100 imputed complete data sets will be generated.

The imputation step of missing data with a monotone pattern will be separated in several sequences:

- For all patients with study or drug premature withdrawals due to other reasons as well as for patients with study or drug premature withdrawals due to lack of efficacy or AE in placebo arm, the regression method (adjusted on the same covariates as the model [1] and considering all longitudinal data of planned visits) will be used to impute missing data (*i.e.* based on patient completers under corresponding treatment arm).
- For patients with study or drug premature withdrawals due to lack of efficacy or AE in S95008 arm, the imputation step will be done sequentially for each time point t separately (W4, W12 and W26) based on placebo patients with non missing data at the timepoint t . The regression method will be adjusted on the same covariates as model [1] except the treatment variable (which is a modified variable in order to consider the placebo data as reference for imputation) and considering all longitudinal data of planned visits up to timepoint t .

It is of note that for missing data with an arbitrary missing pattern, the first imputation step might be preceded by one MI approach based on MCMC method using treatment groups, baseline and variable of interest at the planned visit.

2/ Analysis step:

The same model as [1] (described above) will be applied to each of the 100 imputed datasets.

3/ Combination step:

Statistical inferences will be generated by combining results from the 100 analyses using Rubin's formulae. The multiple imputation estimator of the difference between bumetanide and placebo is the average of the individual 100 estimators. The variance of the estimator is the combination of the between- and within-imputation variability (Carpenter and Kenward, 2007).

Statistical elements: Finally, the following elements will be provided in a summary table:

- Estimate (standard error) of the difference between adjusted treatment arm means.
- Two-sided 95% CI of the estimate.
- Two-sided p-value.

